1. PURPOSE OF STUDY

Neuropsychiatric symptoms (NPS) are a distinctive set of behavioral disturbances that are prevalent in mild cognitive impairment (MCI) and Alzheimer's disease (AD), worsening of which, particularly, can accelerate patients' cognitive and functional decline and cause significant distress to caregivers.^{1,2} NPS often co-exist, rendering the need to understand the shared biological mechanisms underlying multiple NPS, which is crucial for the development of effective interventions to address them simultaneously. Notably, we recently discovered a neural circuit shared by MCI and AD patients with multiple NPS; the circuit is composed of 10 frontal-temporal-striatal regions³ and is highly related to both study partner-rated Neuropsychiatric Inventory Questionnaire (NPI-Q) and AD pathology (indexed by cerebrospinal fluid A β /ptau ratio).³ The **goal of this proof-of-concept mechanistic intervention study** is to confirm the causal relationship between this neural circuit and various NPS, by modifying a key region within the neural circuit [i.e. left precentral gyrus (LPG), critical for regulating visual attention⁴] with anodal transcranial direct current stimulation (tDCS).

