4. STUDY DESIGN

This is a Stage 0 study for mechanistic understanding. We will recruit older adults with study partner-rated NPS that has worsened in the past 2 years. Our previous study shows that this will capture

the most detrimental type of NPS.¹ We will focus on the MCI group, since understanding and modifying NPS among this group may assist in slowing the progression of dementia. See Table 1 for the overview of assessment and intervention timeline.

- Double-blind randomized controlled trial of 40 participants and their study partner subjects; all eligible and interested intervention subjects will be enrolled and undergo a baseline assessment, MRI scan, and blood draw; PI, staff conducting follow-up assessments and intervention subjects and their study partner subjects will be blinded. Interventionists and data managers will know randomization.
- After baseline, all intervention subjects will be randomly assigned to one of two groups - active anodal or sham C3 tDCS. A MATLAB block-based randomization code will be used to randomly assign study ID to group. Each study ID-group pairing will be printed and placed inside a sealed envelope labeled with only the study ID to ensure blinding. After an intervention subject and their partner subject finish baseline assessments, the interventionist or data manager will open the randomization envelope to assign the respective study ID.
- All intervention subjects will undergo a total of fourteen (14) 20-minute tDCS sessions over the course of four weeks: ideally, five times a week for two weeks, followed by twice a week for an additional two weeks. However, we will extend the intervention for additional two weeks for make-up sessions.
- Assessments will occur at baseline, within 2-week after finishing intervention (post-intervention assessment), and 4 to 6 weeks after post-intervention assessment (follow-up assessment).
- Unblinding will occur upon the completion of the follow-up assessment. We will not provide those in the sham group with the active tDCS procedure.

Primary endpoints:

- Resting-state and visual attention task-related fMRI;⁴⁵

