17. DATA ANALYSIS PLAN

This is a pilot study for mechanistic understanding of the relationship between our previously discovered NPS-shared neural circuit and study partner-rated NPS. Results from the study will provide information for accurately calculating effect size for future clinical trial. Regardless, in addition to follow the rule of 12-20 subjects per group for a pilot clinical trial, we will calculate the sample size. The sample size calculation is based on the effect size of LPG related tDCS on visual attention performance ($f = 0.45$, $n = 36$). Additionally, the effect size of correlation between NPS-shared neural circuit and patient-report NPI-Q was $r^2 = 0.70$ in our previous study³ – here we use a much more conservative estimation at $r^2 = 0.20$, the sample size will be $n = 37$. All of these calculations are based on power at 0.80 and alpha at 0.05. For an 8-week follow up, we estimate 10% attrition rate. Therefore, we propose a total of 40 intervention subjects for the study.

Aim 1. Determine the effect of tDCS on NPS-shared neural circuit. H: After intervention, the active, relative to sham group will have greater increase in LPG activity, indexed by greater activation in LPG in response to visual attention task (H1a) and greater increase in resting FC strength between LPG and other regions within the NPS-shared neural circuit (H1b). To assess the activation pattern in LPG, we will conduct GLM analysis with the SPM software. The coefficients of GLM corresponding to LPG will be analyzed through hypothesis testing. We will first conduct a simple t-test to evaluate whether the intervention increases LPG activation for each group (at 4 or 8 weeks), and then a more powerful two sample kernel test will be used to test activations distribution difference between groups.⁵¹ Similarly, we will take the FCs between LPG and other regions as a multivariate covariate and apply the two-sample kernel test to evaluate group difference in the change of LPG FC pattern after intervention (at 4 or 8 weeks). In addition, simple multiple testing for each connection will be used as a screening procedure to identify a subset of connections included in the kernel test.

Aim 2. Determine the relationship between NPS-shared neural circuit and study partner-report NPS.

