H2a. After intervention, the active, relative to sham group will have greater improvement in study partner-rated NPS in terms of lower severity and fewer co-existing symptoms: We will fit linear mixed-effect models for changes in NPS: $Y_i = X_i\beta + Z_iu_i + \epsilon_i$, where $Y_i = (y_{i1}, \dots, y_{iT})$ represents the NPI measures across time, X_i is a $T \times p$ design matrix for the fixed effects and Z_i is a $T \times q$ matrix for the random effects. The models will include fixed effects such as data collection visit (categorical variable), group, visit and group interaction, and covariates identified as being imbalanced among groups. Stepwise variable selection based on Akaike Information Criteria will be used to select the fixed effects for inclusion. A random participant-specific effect will be included to account for correlation between visits for the same participant. The model-based average within-group change will be computed for each outcome at 4 and 8 weeks. This will allow us to rank the groups in terms of average within-person gains in each outcome. We will conduct a composite hypothesis test to assess if the changes at 4 or 8 weeks differ by groups (similar to a one-factor ANOVA but accounting for repeated measures). **H2b. FC change in NPS-shared neural circuit will contribute to the improvement in study partner-rated NPS across groups:** We will perform epsilon-intensive support vector regression (SVR) with RBF kernel using LIBSVM library.⁵² The Leave-One-Out-Cross-Validation scheme will be applied: each intervention subject will be designated as

the test sample once, while the remaining intervention subjects will be used as training sample. All training sample's features (change of voxel activation from the task or change of FCs from the NPS-shared neural circuit after intervention) will be trained to predict the test sample's outcome (change of NPI severity or frequency score). We will then perform model fitting of the raw and predicted NPI using linear function ($f(x)=ax+b$). Adjusted R^2 will be used to estimate goodness of fit for the model.

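### H2b pools both arms with no arm term, so part of its fit could be a shared treatment effect that the plan cannot separate from a circuit–symptom link

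*Combined protocol and SAP*

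**What the plan says.** Section 1 gives the goal as to "confirm the causal relationship between this neural circuit and various NPS". Section 4 has participants "randomly assigned to one of two groups - active anodal or sham C3 tDCS". H1a and H1b predict that active stimulation raises LPG activation and connectivity. H2a predicts that it improves partner-rated symptoms.

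H2b, in section 17, links the two. It states that circuit change "will contribute to the improvement in study partner-rated NPS across groups". The method is a leave-one-out support vector regression with an RBF kernel. Each participant is predicted from a model trained on everyone else, whichever arm they were in. The features are change scores in task activation or in functional connectivity, and the outcome is change in NPI severity or frequency. The result is judged by the adjusted R-squared of a straight line through observed and predicted NPI. No threshold, p value or permutation test is given.

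Arm does not enter H2b at any step. It is used in the H1 comparisons, in the H2a mixed model and in the exploratory comparison of connectivity with white matter. Section 4 names medication changes as confounders for later analyses but does not mention arm. No within-arm or mediation analysis is described anywhere.

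**The concern.** H2b is the only analysis that connects circuit change to symptom change. H1 shows whether tDCS moves the brain measures, and H2a whether it moves symptoms. If both are true, arm is a common cause of H2b's predictor and of its outcome. Two arms that differ on both variables produce a pooled association even when, within each arm, participants whose circuit changed more did no better on the NPI. H2b could then restate H1 and H2a together as a third, mechanistic result.

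Genuine mediation would also produce a pooled association. The weakness is therefore not that a pooled fit must be false, but that the planned analysis gives no means of telling the two explanations apart.

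**Working it through.** **Inputs from section 17.** "All of these calculations are based on power at 0.80 and alpha at 0.05". The circuit–NPS calculation assumes r² = 0.20 and gives n = 37. The tDCS effect is f = 0.45, stated for visual attention performance. "For an 8-week follow up, we estimate 10% attrition rate", and "we propose a total of 40 intervention subjects for the study", so completers are 40 × 0.9 = 36.

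**The plan's own figure.** Fisher z for one correlation, two-sided: r = √0.20 = 0.447, atanh(r) = 0.481, and n = ((1.960 + 0.842)/0.481)² + 3 = 36.9, rounded up to 37. This reproduces.

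**Assumptions.** Equal allocation, 18 per arm (the ratio is not stated). For two equal arms d = 2f, so f = 0.45 corresponds to d = 0.9. That value is borrowed: the documents give no tDCS effect on connectivity change or NPI change, so a range is shown.

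**Induced correlation.** Take one feature, unit within-arm SD, zero within-arm correlation, and arm shifts d1 (brain) and d2 (NPI). Then

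r = (d1·d2/4) / √((1 + d1²/4)(1 + d2²/4)).

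At 0.9 on both, r = 0.2025/1.2025 = 0.168. At 0.9 and 0.5, r = 0.1125/√(1.2025 × 1.0625) = 0.100.

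**Simulation at n = 36.** Adjusted R² = 1 − (1 − r²)(35/34). The test is a two-sided 5% test of the correlation. The plan contains no such test; it serves only as a yardstick.

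| d brain / d NPI | induced r | mean adjusted R² | positive, pooled | positive, arm-adjusted |
|---|---|---|---|---|
| 0.5 / 0.5 | 0.06 | 0.003 | about 6.5% | about 5% |
| 0.9 / 0.5 | 0.10 | 0.01 | about 9% | about 5% |
| 0.9 / 0.9 | 0.17 | 0.03 | about 17% | about 5% |
| 1.2 / 1.2 | 0.26 | 0.07 | about 37% | about 5% |

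At 0.9 on both, the spurious adjusted R² reaches the plan's planning value of 0.20 in under 3% of trials.

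**Several features.** If the features together identify arm perfectly, the spurious R² can approach arm's share of the NPI-change variance, (d2²/4)/(1 + d2²/4): 0.06 at 0.5, 0.17 at 0.9 and 0.36 at 1.5. A leave-one-out RBF support vector regression was simulated with nine features (ten regions, hence nine LPG connections). At d = 0.9 on both, the predicted–observed correlation passed a one-sided 5% cut-off in 26% of trials pooled and 5% after centring within arm. At d = 0.5 the rates were 9% and 6%. This assumes nine independent connections, all shifted equally. At 0.9 each, that is a combined separation of 0.9 × √9 = 2.7 SD, which the documents do not support, so it shows direction only.

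**Cost of adjusting if mediation is complete.** Let NPI change = b × brain change + error with unit SD, and fix the pooled r² at 0.20. Then b²(1 + d1²/4) = 0.25.
- d1 = 0.9: b² = 0.25/1.2025 = 0.208. Within-arm r² = 0.208/1.208 = 0.172. Power is about 0.80 pooled and 0.72 adjusted.
- d1 = 1.5: b² = 0.25/1.5625 = 0.16. Within-arm r² = 0.16/1.16 = 0.138. Adjusted power is about 0.61.

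**The case against.** The strongest reply is that pooling is deliberate. The hypothesis is worded for both groups together, the study is a pilot on mechanism, NPS is a secondary endpoint, and the arm contrasts are tested separately under H1 and H2a. Pooling is indeed reasonable for a sample of this size. But it can be kept while arm is accounted for, and the separate tests do not show what the pooled fit measures.

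A second reply is that the bias may be small. This stands in part. With d near 0.5 on the NPI it is slight, and on the plan's own metric the single-feature inflation averages about 0.03 even at 0.9 on both measures. Under full mediation with d = 0.9 on brain and pooled r² of 0.20, the implied NPI effect is only 0.456 × 0.9/√1.208 = 0.37, in the range where the inflation is slight.

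A third reply is that the between-arm part is the only randomised variation in brain change, while the within-arm association is observational. This also stands. A reader might infer that the pooled fit should be demoted to description and H2b judged on the adjusted fit alone. That goes too far: neither fit settles causation, and adjusting costs power that grows with the effect of stimulation on the brain measures.

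**Conclusion.** The point holds as a limit on interpretation. H2b as written cannot separate a circuit–symptom link from a treatment effect shared by both measures, and nothing elsewhere in the plan supplies the missing check.

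The size depends on effects that the documents do not give. With one feature, 36 completers, equal arms and no within-arm link, the spurious adjusted R-squared averages from about 0.003 (d = 0.5 on both) to 0.07 (d = 1.2 on both). With no arm effect on one of the measures there is no such bias. Several features that jointly mark arm could make it larger.

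A reader might infer that a pooled association is bound to appear even when circuit and symptoms are unrelated, or that a positive H2b would be an artefact. The documents do not support either. They give no tDCS effect on connectivity or NPI and no decision rule for H2b. On the yardstick test, about 83% of trials stay negative at d = 0.9 on both measures. The result could mislead; it need not.

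**What to change.** Keep the pooled support vector regression as planned and pre-specify an arm-adjusted fit beside it:

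- In each leave-one-out fold, estimate arm means of every feature and of NPI change from the training participants only. Subtract them from the training data and from the held-out participant's features and outcome.
- Report adjusted R-squared for both fits, with a permutation reference that shuffles outcomes within arm.
- State that circuit change will not be said to contribute to symptom improvement beyond a shared treatment effect unless the arm-adjusted fit supports it.
- State that arm adjustment removes confounding by arm but does not by itself prove causation, since other causes of both brain change and symptom change may remain.

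No new data are needed: section 4 has data managers knowing the allocation and unblinding after the follow-up assessment. The cost is a short addition to section 17, a little more analysis, and lower power for the adjusted fit if the circuit fully mediates the effect: from about 0.80 to 0.72 at d = 0.9 on brain and to 0.61 at d = 1.5, with pooled r² of 0.20. That loss is a reason to report both fits.

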Why focus on the LPG via tDCS to understand the contribution of this shared neural circuit to NPS? Our previous work on NPS-shared neural circuit shows that while different NPS are associated with the same 10 frontal-temporal-striatal regions, the strength of functional connectivity (FC), as well as its directionality, varies for different NPS. For example, the strength of most FCs in MCI/AD patients with a depressive symptom is lower than that in patients without this symptom, while the strength of most FCs are higher in patients with an anxiety symptom. Across NPS, however, LPG is the only region that has lower FCs with frontal and striatal regions within the circuit whenever a NPS is present.³ LPG, parallel to C3 in the 10/20 EEG system,⁵ is one of the most frequently examined and effective tDCS targets modifying affective, psychiatric, and psychosomatic symptoms, in addition to motor function.⁶⁻⁸ Administering anodal tDCS also enhances the strength of FCs linking LPG to frontal and limbic regions that are part of the NPS-shared neural circuit.⁹⁻¹² Notably, our feasibility study demonstrated our readiness and safety of administering anodal tDCS to C3 in older adults. Synthesizing these separate lines of evidence, we **hypothesize** that administering anodal tDCS to C3 in patients with NPS will result in enhanced activation of LPG and reorganization of NPS-shared neural circuit, both of which will improve NPS.

Aim 1. Determine the effect of tDCS on NPS-shared neural circuit. **H:** After intervention, the active group, relative to the sham group, will have a greater increase in LPG activity, indexed by greater activation in LPG in response to a visual attention task (H1a) and greater increase in resting FC strength between LPG and other regions within the NPS-shared neural circuit (H1b).

Aim 2. Determine the relationship between NPS-shared neural circuit and study partner-report NPS. **H:** After intervention, the active group, relative to the sham group, will have greater improvement in study partner-rated NPS in terms of lower severity and fewer co-existing symptoms (H2a). Changes in LPG task-induced activity combined with an LPG-seeded NPS-shared neural circuit will contribute to the

improvement in study partner-rated NPS across groups (H2b).

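### H2b reports only a goodness-of-fit score that stays the same when every brain change is reversed in sign, so a good score cannot by itself support the claim that enhancing LPG improves NPS

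*Combined protocol and SAP*

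**What the plan says.** Section 1 gives the overall hypothesis a direction: anodal stimulation is expected to produce "enhanced activation of LPG and reorganization of NPS-shared neural circuit, both of which will improve NPS". H1a and H1b accordingly predict increases in LPG task activation and in LPG resting connectivity. H2b then links the brain changes to the change in study partner-rated NPS, across both groups.

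Section 17 (Aim 2, H2b) gives this link one analysis:

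- Method: "We will perform epsilon-intensive support vector regression (SVR) with RBF kernel using LIBSVM library".
- Validation: "The Leave-One-Out-Cross-Validation scheme will be applied".
- Features: "change of voxel activation from the task or change of FCs from the NPS-shared neural circuit after intervention".
- Outcome: "change of NPI severity or frequency score".
- Summary: "We will then perform model fitting of the raw and predicted NPI using linear function", after which adjusted R-squared "will be used to estimate goodness of fit for the model".

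No coefficient, weight map, partial-dependence plot or mediation model is named for H2b. The other brain-to-NPI analyses in Section 17 belong to the exploratory aim and the blood analysis. They use structural connections, baseline white-matter tracts or blood markers, not change in LPG activation or connectivity.

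**The concern.** The theory is that more LPG activity goes with fewer or milder symptoms. The single number that H2b reports measures how closely predicted NPI change follows observed NPI change. It does not show whether participants with larger LPG increases improved or deteriorated.

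Section 1 sets out to confirm a causal relation between circuit and symptoms, and intends to carry a validated result into a Stage 2 trial. If a good H2b score is read as support for that mechanism, an inverse relation (larger LPG increase, worse NPI) would be read in the same way, and nothing in the planned output would reveal it.

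**Working it through.** **Inputs.** Method, features, outcome and summary are from Section 17 (H2b). The circuit has 10 regions including LPG (Section 1), so there are 9 LPG connections. The planned total is 40 with 10% attrition (Section 17), which gives 40 × 0.90 = 36 completers. The circuit-to-NPI effect size is r² = 0.20, with power 0.80 and alpha 0.05 (Section 17).

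**1. The plan's own figure.** For one correlation, two-sided, by Fisher z: n = ((1.960 + 0.842) / atanh(√0.20))² + 3. With atanh(0.447) = 0.481, this is 36.9, so 37. The stated n = 37 is reproduced.

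**2. Why the score has no sign.** The RBF kernel is K(u,v) = exp(-γ‖u - v‖²). Since ‖(-u) - (-v)‖ = ‖u - v‖, the kernel matrix is the same for the brain changes X and for -X. The SVR predictions depend only on that matrix and on NPI change, so the predictions, the fitted line and adjusted R-squared are all unchanged.

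**3. The same holds for other models.** A linear kernel has (-u)·(-v) = u·v. Ordinary regression has the same fitted values for X and -X. In one check with nine predictors, ordinary R-squared was 0.1188 for both. The invariance belongs to goodness-of-fit scores in general.

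**4. Numerical check.** Simulated data, n = 36, leave-one-out.

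- LIBSVM, RBF kernel, nine features, 50 data sets with true r² = 0.20: the largest difference between predictions from X and from -X was 0. It was also 0 in a run with tuned C and γ.
- Worked example, nine features: the correlation of raw with predicted NPI change was 0.658. Adjusted R-squared = 1 - (1 - 0.658²) × 35/34 = 0.416, for X and for -X alike. The fitted slope was 1.076 for both. The correlation of mean brain change with NPI change was -0.757 for X and +0.757 for -X.
- Reversing NPI change instead of the brain changes also gave 0.416.

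**5. Can direction be recovered?** Yes, from the fitted function. In the same example, prediction at +1 minus prediction at -1 was -2.476 for X and +2.476 for -X. The plan does not report this quantity.

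**6. What a signed test could do.** If LPG activation change and NPI change have |r| = 0.447 (an assumption, borrowed from r² = 0.20), two-sided power by Fisher z is Φ(0.481 × √(n - 3) - 1.960): 78.9% at n = 36, 80.1% at n = 37 and 83.3% at n = 40. At n = 36 the chance of significance in the wrong direction is Φ(-1.960 - 2.764), about 0.0001%.

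**7. Why not simply average the connections?** Assume nine independent, equally weighted LPG connections with joint r² = 0.20 and n = 36. If k of them run opposite to the rest, the correlation of the unweighted mean with NPI change is 0.447 × (9 - 2k)/9.

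| Opposite connections | r | Power in the expected direction |
|---|---|---|
| 0 | 0.447 | 79% |
| 2 | 0.248 | 31% |
| 4 | 0.050 | 5% |

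**The case against.** Several points on the other side have force.

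- **The kernel is not at fault.** A reader might infer that the RBF kernel makes H2b blind to sign and that another model would cure it. Steps 3 and 5 show otherwise: other fit scores share the invariance, and the fitted RBF function does carry direction. This stands. What remains is that the plan names no output showing the direction.
- **H2b is not worded as a sign hypothesis.** It claims only that the brain changes play a part in the improvement. Section 1 says that connectivity strength and direction differ between symptoms and speaks of reorganization. Section 2 describes stronger LPG connectivity with some regions and weaker with others. The SVR features may also include circuit connections that do not involve LPG. This stands for connectivity. For activation, Section 1 is directional, although Section 2 indexes it by neural efficiency, which is another reason to write the expected sign down.
- **H1 and H2a supply direction.** They do so for group averages. LPG could rise and NPI fall on average while, across participants, larger rises went with worse NPI. H2b is the participant-level claim, so this does not close the gap.
- **The sample-size basis.** A reader might infer that n = 37 was computed for a correlation that H2b never calculates. Section 17 says only that "the effect size of correlation between NPS-shared neural circuit and patient-report NPI-Q was" 0.70 in an earlier study, then takes 0.20. It does not say how that r² was obtained, and H2b's own summary is an r²-type quantity. The documents do not support that inference.
- **Weight.** This is a Stage 0 pilot, NPS is a secondary endpoint, and H2b is an across-group association. Even a signed slope would not prove causation. This stands and limits the importance of the point.

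**Conclusion.** The concern holds in a limited form. H2b's only named output is exactly unchanged when all brain changes are reversed, and Section 17 has no other signed participant-level link between change in LPG activation or connectivity and change in NPI. As written, the plan could count an inverse relation as support for the directional theory in Section 1.

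The invariance is algebraic and rests on no simulation setting. The power figures do rest on assumptions: linear relations, r² = 0.20, 36 completers and, for the averaged connections, independence and equal weights.

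It would go too far to say that the analysis can never reveal direction, or that any result opposite in sign would contradict H2b as worded. The fitted model holds the direction, and for connectivity the documents leave the expected sign mixed. The defect is a missing output and a missing rule for reading it. It is worth correcting because the correction is cheap.

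**What to change.** 1. Keep the SVR as planned.
2. Add a pre-specified linear regression of NPI change on change in LPG task activation, using the same change scores as the SVR. Report the slope with its 95% CI, and state the expected sign in advance: larger increase, larger NPI reduction.
3. For connectivity, report signed slopes for the LPG connections, or a partial-dependence output from the fitted SVR. Fix the expected sign for each connection beforehand from the prior circuit findings, and do not rely on an unweighted mean.
4. State the reading rule: conclude that enhancing LPG improves NPS only if the direction agrees; otherwise report H2b as a non-directional association.

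The cost is SAP wording and a few regressions on data already being collected. The downside is small: the slopes assume approximate linearity, and they add a few secondary estimates. The SVR remains available for non-linear patterns.

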fMRI data will be collected using a gradient echo-planar imaging sequence. Participants will undergo a 5-minute resting-state scan at first, being instructed to relax with their eyes open, followed by a 5-minute event-design ‘target among distractors’ visual search task. For the task, participants fixate on a black screen for a constant inter-stimulus interval of 1000ms, follow by 5500ms presentation of the search pattern. Participants’ task is to search for target symbol “申” (which was present for 50% of trials), shown among 6 distractors (e.g., “由”, “甲”, etc.). Participants are instructed to press one of two response buttons to indicate whether the target was present or absent.

Secondary endpoints:

- Study partner-rated NPS (frequency and severity scores from NPI and NPI-Q⁴⁶).

Other measures:

- Cognitive functions will be measured using tests from three different versions of the computer-based battery Executive Abilities: Measures and Instruments for Neurobehavioral Evaluation and Research (EXAMINER);
- Paper-based measures of cognitive functioning will be measured using two versions of the Rey Auditory Verbal Learning Test (RAVLT, Lists A&B and C&D) and the Brief Visuospatial Memory

Test-Revised (BVMT-R, Forms 1-3);

- Functioning in daily life will be measured with the self-report version of the Activities of Daily Living-Prevention Instrument (ADL-PI-self).
- Fatigue across 5 domains (general, physical, mental, and reduced motivation & reduced activity) will be measured using the Multidimensional Fatigue Inventory (MFI);
- Sleep habits and quality of sleep will be measured using the total score from the Pittsburgh Sleep Quality Index (PSQI);
- Depression will be measured using both the 15- and 30-item versions of the Geriatric Depression Scale (GDS);
- Risk of suicide (current & past) and current suicidal ideation will be measured using Columbia Suicide Severity Rating Scale (C-SSRS);
- Anxiety will be measured using both the state and trait anxiety scales from the State-Trait Anxiety Inventory (STA);
- Perception of stress will be measured using Perceived Stress Scale (PSS);
- Apathy will be measured using the 18-item self-report and informant-rated Apathy Evaluation Scales (AES);
- Quality of life (QoL) across multiple life domains (including physical health, mood, relationships, activities, ability to perform tasks) will be measured using the 13-item self-report and informant-rated Quality of Life in Alzheimer's Disease scales (QOLAD);

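### H2b is worded differently in Sections 1 and 17, no combined activation-plus-connectivity model is specified, and the reported result can be chosen from up to four fits with no inferential criterion

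*Combined protocol and SAP*

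**What the plan says.** Section 1, Aim 2, gives H2b as a statement about two imaging measures taken together: "Changes in LPG task-induced activity combined with an LPG-seeded NPS-shared neural circuit will contribute to the" improvement in partner-rated NPS, across groups.

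Section 17, Aim 2, gives H2b a different title: "FC change in NPS-shared neural circuit will contribute to the improvement in study partner-rated NPS across groups". Task activity and the idea of combination are both absent.

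The method under that title is an epsilon-SVR with RBF kernel and leave-one-out cross-validation. Its features are "change of voxel activation from the task or change of FCs from the NPS-shared neural circuit after intervention". Its outcome is "change of NPI severity or frequency score". Observed and predicted NPI are then fitted with a straight line, and adjusted R-squared "will be used to estimate goodness of fit for the model".

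Three other places bear on the point:
- Section 4 lists the secondary endpoint as "Study partner-rated NPS (frequency and severity scores from NPI and NPI-Q"), so both scores are declared parts of the NPS construct.
- Table 1 schedules MRI and the full NPI at both post-intervention visits. The H2a test is to "assess if the changes at 4 or 8 weeks differ by groups"; the H2b text says only that change is measured after intervention.
- The sample-size paragraph of Section 17 covers the circuit-NPS relation as a single correlation: "here we use a much more conservative estimation at $r^2 = 0.20$, the sample size will be $n = 37".

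**The concern.** H2b carries the mechanistic claim of the study, that change in the circuit accounts for change in symptoms. The aim and the analysis section describe different hypotheses, and the listed features are offered as alternatives. An analyst who follows Section 17 literally can complete it without fitting any model that addresses the joint claim in Section 1.

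The same wording leaves the choice of feature set, outcome and visit open until the data are seen. The fit that looks best could then be reported as support for H2b. Section 17 says the results are meant to inform effect sizes for a later trial, and an estimate picked as the best of several would tend to be too large.

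**Working it through.** **1. The versions of H2b side by side**

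| Place | Predictor | Outcome |
|---|---|---|
| Section 1, Aim 2 | LPG task activity and LPG-seeded circuit, combined | Partner-rated NPS |
| Section 17, H2b title | Connectivity change in the circuit | Partner-rated NPS |
| Section 17, H2b method | Voxel activation change or circuit connectivity change | NPI severity or frequency |

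The method also drops the restriction to LPG. Task voxels are not limited to that region, and circuit connections are not limited to those seeded there. Section 1 gives the circuit 10 regions including LPG. That is 9 LPG-seeded connections, against 10 × 9 / 2 = 45 pairwise connections in the whole circuit.

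**2. How many fits the wording allows**

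2 feature sets × 2 outcomes = 4. If both post-intervention visits are used (an assumption, since H2b names no visit), 4 × 2 = 8. These are upper counts for the listed alternatives; an analyst could run only one.

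**3. What can be said about false positives**

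The plan gives H2b no null hypothesis, p-value or threshold, so no error rate follows from it. For illustration, suppose each fit were tested at 5% and the tests were independent:
- four fits: 1 − 0.95^4 = 0.185
- eight fits: 1 − 0.95^8 = 0.337

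The fits share participants, instrument and scans, so independence is not realistic. With complete dependence the rate would be 5%. The bounds that need no independence assumption are 4 × 0.05 = 20% and 8 × 0.05 = 40%.

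**4. Why adjusted R-squared alone does not serve as a test**

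Take the limiting case of a rule that ignores the imaging and predicts each left-out participant by the mean of the others. With n participants the prediction is (n × mean − y_i)/(n − 1), an exact straight line in the observed value y_i with slope −1/(n − 1). At n = 36 the slope is −1/35 = −0.029 and R-squared is 1, although nothing has been predicted. The planned SVR is not this rule. The case shows only that the written criterion does not exclude a high R-squared that comes from an inverse relation.

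**5. The plan's own sample size, and what a joint model might cost**

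Inputs from Section 17: r² = 0.20, power 0.80, alpha 0.05, N = 40, attrition 10%. Sidedness is not stated; two-sided is assumed.

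Fisher z: n = ((1.960 + 0.842)/atanh(√0.20))² + 3 = (2.802/0.4812)² + 3 = 36.9, so 37. This reproduces the stated figure. It applies to one correlation, not to a combined predictor set.

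Expected completers: 40 × 0.90 = 36.

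As a linear stand-in, use the fixed-predictor F test with f² = 0.20/0.80 = 0.25 and noncentrality f² × n:

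| Predictors | n for power 0.80 | Power at n = 36 |
|---|---|---|
| 1 | 34 | 0.83 |
| 2 (one activation, one connectivity summary) | 42 | 0.73 |

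The comparison holds total R² at 0.20. If the second predictor adds explained variance, the loss is smaller. It does not give the power of the SVR.

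**The case against.** A reader might infer that the plan never tests H2b. The documents do not support that. In the feature list, the word joining activation and connectivity can be read inclusively, and it does not forbid entering both. Section 17 also has its own connectivity-only H2b, which the connectivity-feature SVR does address. What stands is narrower: the two statements of H2b differ, and no combined model is specified. An inclusive reading only adds another unselected option.

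A reader might infer that at least four models will be run. The text does not require every alternative, so four is a maximum for one visit.

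A reader might also count the two outcomes as a reason the hypothesis goes untested. Section 4 makes frequency and severity both part of partner-rated NPS, so either is a legitimate outcome. The open choice between them is a selective-reporting problem.

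Finally, this is a Stage 0 mechanistic pilot, NPS is a secondary endpoint, and no stated number is wrong because of this point. That limits the weight of the finding. It does not remove the mismatch between the aim and its analysis, which is cheap to correct.

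**Conclusion.** The point holds as one of specification. Sections 1 and 17 state H2b differently. Section 17 commits to no model with both feature sets, and the result reported for H2b can be drawn from up to four fits, or eight if both visits are used. The one criterion is a goodness-of-fit measure with no null, threshold or required direction.

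It would be tempting to say that H2b has a 19% or 34% false-positive rate. Those figures rest on a 5% test and on independence, neither of which the plan states, and should be read as illustrations. The counts of four and eight rest only on the listed alternatives and on Table 1. The matter should be settled before outcome data are analysed.

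**What to change.** 1. Use the Section 1 wording of H2b in Section 17.
2. Make one SVR the H2b analysis, with LPG activation change and LPG-seeded connectivity change entered together. State openly that this narrows the features from the task voxels and circuit connections now listed.
3. Pre-specify one NPI outcome and one visit, for example severity at the post-intervention visit. Which is chosen matters less than that it is fixed in advance.
4. Report activation-only, connectivity-only and other-outcome models as secondary, to show what each measure contributes.
5. Judge the leave-one-out prediction by a permutation test: shuffle the outcome changes across participants, rerun the whole procedure including any tuning, and count as support only a positive relation between predicted and observed change. Adjusted R-squared can stay as a description.

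The cost is revised wording, one joint model and the permutation runs, all on data already planned. A joint model may have lower power at about 36 completers, and this should be acknowledged in the plan.
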